MRI brain	X ^f						X	All brain scans on protocol are required to be MRI unless MRI is contraindicated, then CT with contrast is acceptable. Subsequently after screening, MRI brain can be performed at any time if clinically indicated per standard of care.

Footnotes defined on last page of this table.

Table 1-1. Schedule of Activities: Cycle 1 only

Procedure ^a	Screening	Treatment Period ^b					As clinically indicated	Notes
		Cycle 1						
Day	(Up to 21 Days Before Day 1)	1	2	8	9	15		
Radiological imaging and tumor assessment ^g	X ^f	Weeks 1 to 48: Q6W (± 1 week) Weeks 49+ Q12W (± 1 week) by BICR per RECIST 1.1					X	Refer to Section 8.3.1 for additional details. For subjects who end study treatment for reasons other than specified in Section 8.3.2, every effort should be made to perform scheduled radiographic imaging (CT/MRI) until radiographic progression.
STUDY TREATMENT AND MONITORING								
Other protocol-required therapy: Dexamethasone		X		X				Refer to Section 6.1.2 for details for pre-treatment with dexamethasone (or equivalent dose of other corticosteroids). Dexamethasone will be administered within 1 hour prior to tarlatamab infusion on days 1 and 8 of cycle 1 only.
Tarlatamab Infusion		X		X		X		

Footnotes defined on last page of this table.

Table 1-1. Schedule of Activities: Cycle 1 only

Procedure ^a	Screening	Treatment Period ^b					As clinically indicated	Notes
		Cycle 1						
Day	(Up to 21 Days Before Day 1)	1	2	8	9	15		
Monitoring post-tarlatamab infusion		X		X			X	Subject will remain at study site for 6 to 8 hours post-infusion at C1D1 and C1D8 Cohabitant (caregiver) support for 24 hours post-infusion and the ability to stay within 1 hour of a hospital for 24 hours is required. Counseling the subject and caregiver on signs and symptoms of CRS and ICANS by a health care provider is required prior to discharge. Subjects return to site on C1D2 and C1D9 for vital signs and physical examination. At subsequent visits, additional monitoring may be recommended post-tarlatamab infusion based on occurrence of CRS, ICANS, or ICANS-related neurological events. Refer to Table 6-1 .
Other protocol-required therapy: IV hydration		X		X				Refer to Section 6.1.2 for details related to IV hydration. IV hydration (1 L normal saline) over 2 to 4 hours following tarlatamab administration.

Page 5 of 5

BICR = Blinded Independent Central Review; C1D1 = cycle 1 day 1; C1D2 = cycle 1 day 2; C1D8 = cycle 1 day 8; C1D9 = cycle 1 day 9;

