6.1 Study Interventions Administered

6.1.1 Investigational Products

Table 6-1. Investigational Products

Study Treatment Name	Amgen Investigational Product:^a Tarlatamab (AMG 757)
Dosage Formulation	Tarlatamab is supplied as a sterile, single-use, preservative-free lyophilized drug product containing 1 or 10 mg of tarlatamab per vial. Tarlatamab is intended for reconstitution with sterile water for injection and dilution in an IV bag with normal saline (0.9% sodium chloride) and an IV solution stabilizer. The drug product is formulated with L-glutamic acid, sucrose, polysorbate 80, pH 4.2.
Dosage Level(s)	1 mg step dose on C1D1 10 mg target dose starting C1D8, C1D15, and Q2W thereafter
Route of Administration	IV infusion
Accountability	Product administration information is to be recorded on each subject's eCRF(s).
Dosing Instructions	Tarlatamab will be administered as an IV infusion for 60 minutes (\pm 10 minutes) followed by a slow bolus flush. Investigational products will be administered at the study center by a qualified staff member. A physician must be available at the time of administration of investigational products.

Page 1 of 2

Footnotes defined on last page of this table.

Table 6-1. Investigational Products

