Monitoring Guidance	
 • Cycle 1 Day 1 and Cycle 1 Day 8: 
 ○ Subject will remain at study site for 6 to 8 hours post-infusion at C1D1 and C1D8. Cohabitant (caregiver) support for 24 hours post-infusion and the ability to stay within 1 hour of a hospital for 24 hours is required. ○ Subjects may be discharged after the required monitoring period if there are no signs and symptoms of CRS, ICANS, or other acute toxicities according to the discretion of the treating physician. Counseling the subject and caregiver on the signs and symptoms of CRS and ICANS by a healthcare provider is required prior to discharge. • Subjects return to site on cycle 1 day 2 and cycle 1 and day 9 for vital signs and physical examination. • Monitoring for subsequent treatment visits is at the discretion of the investigator if asymptomatic and clinically stable. Consider monitoring if the subject experiences a grade ≥ 2 CRS, any grade ICANS, or any grade ICANS-related neurologic^b adverse events at the immediate prior treatment (ie, following the dose given at the prior visit). 
 – Refer to the C1D1 requirements above. 
In the event of an extended study treatment interruption (see Table 6-3), subjects are required to be monitored according to cycle 1 monitoring guidance.

----------------------------	---

Page 2 of 2

C1D1 = cycle 1 day 1; C1D8 = cycle 1 day 8; C1D15 = cycle 1 day 15; CRS = cytokine release syndrome; eCRF = electronic case report form;

ICANS = immune effector cell-associated neurotoxicity syndrome; IV = intravenous; Q2W = every 2 weeks

^a Tarlatamab will be manufactured and packaged by Amgen and distributed using Amgen clinical study drug distribution procedures.

^b ICANS-related neurologic adverse events per discretion of investigator, which may include, but are not limited to confusion, delirium, encephalopathy, apraxia, ataxia, neurotoxicity, seizure, tremor, dysgraphia, expressive aphasia, depressed level of consciousness, or impaired attention.

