6.2.2 Dosage Adjustments, Delays, Rules for Withholding or Restarting, Permanent Discontinuation

6.2.2.1 Amgen Investigational Product: Tarlatamab

The reason for dose change of tarlatamab is to be recorded on each subject's CRF(s).

Tarlatamab will be discontinued or temporarily delayed in the event of a toxicity that, in the opinion of the investigator, warrants the discontinuation or dose delay. For treatment interruptions, delays, and discontinuations, refer to tarlatamab guidance in [Table 6-2](#).

Table 6-2. Tarlatamab Dose Modification Guidelines for Adverse Events

Grade	Description of Severity	Interruption/Delay	Specific Management	Restart guidance	Permanent Discontinuation
Neurologic Events					
1	Reference Section 11.11.2 for grading and management guidelines	No additional guidance	Follow institutional guidelines for management and per local practice: 
 Consider diagnostic workup for alternate diagnosis^a Supportive Care 	No additional guidance	No additional guidance
2		No additional guidance	Follow institutional guidelines for management and administer corticosteroids per local practice: 
 Consider diagnostic workup for alternate diagnosis^a Reference dose of corticosteroids for grade 2 ICANS ^a : 
 Dexamethasone 8 mg to 10 mg IV every 12 hours or methylprednisolone equivalent. Once ICANS improves to grade 1 or less, taper and/or stop corticosteroids depending on clinical situation 	No additional guidance	No additional guidance
3		Delay tarlatamab until the event improves to grade ≤ 1	Follow institutional guidelines for management and administer corticosteroids per local practice: 
 Consider diagnostic workup for alternate diagnosis^a Consider ICU transfer Reference dose of corticosteroids for grade 3 ICANS ^a : 
 Dexamethasone 10 mg IV every 6 hours or methylprednisolone equivalent (1 mg/kg IV every 12 hours). Once ICANS improves to grade 1 or less, taper and/or stop corticosteroids depending on clinical situation 	Resume tarlatamab no less than 72 hours after the initial observation of the grade 3 adverse event	
 Initial grade 3 neurologic event does not improve to grade ≤ 1 within 7 days, OR Grade 3 neurologic event reoccurs within 7 days of resuming tarlatamab

Abbreviations and footnotes defined on last page of table.

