3 ^f	Delay tarlatamab until the event improves to grade ≤ 2	
 Assess for other potential etiologies of neutropenia, including concomitant medications and underlying infection Consider bone marrow biopsy, anti-neutrophil antibodies Granulocyte colony-stimulating factor (G-CSF) administration is permitted 	Resume tarlatamab no less than 72 hours after the initial observation of the grade 3 adverse event	No additional guidance
4 ^f	Delay tarlatamab until the event improves to grade ≤ 2	
 Assess for other potential etiologies of neutropenia, including concomitant medications and underlying infection Consider bone marrow biopsy, anti-neutrophil antibodies Consider G-CSF administration 	Resume tarlatamab no less than 72 hours after the initial observation of the grade 4 adverse event	Initial grade 4 nonfebrile neutropenia event lasts > 7 days OR Grade 4 event reoccurs

Abbreviations and footnotes defined on last page of table.

Table 6-2. Tarlatamab Dose Modification Guidelines for Adverse Events

Grade	Description of Severity	Interruption/Delay	Specific Management	Restart Guidance	Permanent Discontinuation
Hypersensitivity (Allergic Reactions)					
1	Systemic intervention not indicated	No additional guidance	Follow institutional guidelines for management	No additional guidance	No additional guidance
2	Oral intervention indicated	Immediately pause any ongoing infusion	Follow institutional guidelines for management and administer oral antihistamines and/or corticosteroids per local practice.	Restart current infusion of remaining dose at lower rate per local practice if event has resolved	No additional guidance

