
 • Monitor for signs and symptoms of pituitary gland dysfunction. Consider the following studies as indicated: TSH, FSH, LH, cortisol, FT4, testosterone/estradiol, ACTH, prolactin, and IGF-1 
 – Abnormal hormone monitoring result or clinical suspicion of pituitary gland dysfunction (headache, fatigue, asthenia, impaired vision, vomiting, hypotension, amenorrhea, impotence) – Diagnostic tests: brain MRI (if clinically indicated), blood pressure, glycemia, plasma and urine osmolality, electrolytes, laboratory values (ACTH, TSH, FSH, LH, IGF-1, plasma cortisol, FT4, prolactin, testosterone/estradiol) • Urgent endocrinology consultation to guide management of the event • Once pituitary gland dysfunction is confirmed, delay scheduled dose of tarlatamab • Once residual related toxicity \leq grade 2, clinically stable on replacement therapy and < 10 mg prednisone or equivalent, resume tarlatamab • Continue endocrinological surveillance
Hepatotoxicity
For Stopping and Rechallenge Rules, please refer to Section 11.7.

Page 12 of 12

ACTH = adrenocorticotrophic hormone; BiPAP = bi-level positive airway pressure; CARTOX = CAR-T-cell therapy-associated TOXicity; CRS = cytokine release syndrome; CPAP = continuous positive airway pressure; ECHO = echocardiogram; FSH = follicle-stimulating hormone; FT4 = free T4; G-CSF = granulocyte colony-stimulating factor; ICANS = immune effector cell-associated neurologic syndrome; IGF-1 = insulin-like growth factor 1; IL-6 = interleukin 6; IV = intravenous; IVF = intravenous fluid(s); LH = luteinizing hormone; MRI = magnetic resonance imaging; OS = overall survival; PS = performance status; TLS = tumor lysis syndrome; TSH = thyroid-stimulating hormone

^a Based on Immune Effector Cells Therapy Toxicity Assessment and Management (also known as CARTOX) <https://www.mdanderson.org/documents/for-physicians/algorithms/clinical-management/clin-management-cytokine-release-web-algorithm.pdf>

^b American Society for Transplantation and Cellular Therapy (ASTCT) grading system for CRS (Lee et al, 2019).

^c Fever is defined as temperature $\geq 38^{\circ}\text{C}$ not attributable to any other cause. In subjects who have CRS then receive antipyretic or anticytokine therapy such as tocilizumab, siltuximab, or steroids, fever is no longer required to grade subsequent CRS severity. In this case, CRS grading is driven by hypotension and/or hypoxia.

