^d CRS grade is determined by the more severe event: hypotension or hypoxia not attributable to any other cause. For example, a subject with temperature of 39.5°C , hypotension requiring 1 vasopressor, and hypoxia requiring low-flow nasal cannula is classified as grade 3 CRS.

^e Low-flow nasal cannula is defined as oxygen delivered at ≤ 6 L/minute. Low-flow also includes blow-by oxygen delivery, sometimes used in pediatrics. High-flow nasal cannula is defined as oxygen delivered at > 6 L/minute.

^f For neutropenia adverse events grade ≤ 2 , please follow institutional guidelines for management.

For all other treatment interruptions or delays, restart tarlatamab in accordance with the following guidelines in [Table 6-3](#):

Table 6-3. Step dose Rechallenge Requirement After Tarlatamab Delay

Last Dose Administered	Duration of Delay from the Last Dose Administered	Action
Step dose (1 mg)	≤ 14 days	Proceed with tarlatamab 10 mg target dose and then continue treatment Q2W.
	> 14 days	Repeat tarlatamab 1 mg step dose per cycle 1 guidelines, including pre-medication and monitoring requirements (refer to Table 6-1).
First target dose (10 mg)	≤ 21 days	Proceed with tarlatamab 10 mg target dose and then continue treatment Q2W.
	> 21 days	Repeat tarlatamab 1 mg step dose schedule per cycle 1 guidelines, including pre-medication and monitoring requirements (refer to).
Any subsequent target dose (10 mg)	≤ 28 days	Proceed with tarlatamab 10 mg target dose and then continue treatment Q2W.
	> 28 days	Repeat tarlatamab 1 mg step dose per cycle 1 guidelines, including pre-medication and monitoring requirements (refer to Table 6-1).

Q2W = every 2 weeks.

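### Read literally, the lead-in to Table 6-3 takes Table 6-2 toxicity delays out of the repeat step-dose rule, leaving restart dose and premedication unstated after some long holds

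*Protocol*

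**What the plan says.** Protocol Section 6.2.2.1 deals first with toxicity: "For treatment interruptions, delays, and discontinuations, refer to tarlatamab guidance in" Table 6-2. Directly after the footnotes of that table comes the sentence "For all other treatment interruptions or delays, restart tarlatamab in accordance with the following guidelines in" Table 6-3.

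Table 6-3 works by the last dose given and the days since then. Up to 14 days after the step dose, 21 days after the first 10 mg dose, or 28 days after any later 10 mg dose, treatment goes on at 10 mg. Beyond the limit, the step-dose row says: "Repeat tarlatamab 1 mg step dose per cycle 1 guidelines, including pre-medication and monitoring requirements". The other two rows say the same in substance.

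The Table 6-2 entries at issue read as follows:

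- **Grade 3 non-febrile neutropenia:** hold until grade 2 or lower, then "Resume tarlatamab no less than 72 hours after the initial observation of the grade 3 adverse event". The permanent-discontinuation cell adds nothing.
- **Pituitary dysfunction:** once residual toxicity is grade 2 or lower and the patient is "clinically stable on replacement therapy and < 10 mg prednisone or equivalent, resume tarlatamab".
- **TLS:** resume only if it resolves within 14 days, after consulting the medical monitor, and with first-dose monitoring.

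None of the three states a restart dose or premedication, or points to Table 6-3.

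Elsewhere, Table 6-1 sets the dose as "10 mg target dose starting C1D8, C1D15, and Q2W thereafter". The Schedule of Activities (Section 1.3) says: "Dexamethasone will be administered within 1 hour prior to tarlatamab infusion on days 1 and 8 of cycle 1 only". Table 6-1 also says: "In the event of an extended study treatment interruption (see Table 6-3), subjects are required to be monitored according to cycle 1 monitoring guidance". Table 8-1 likewise ties vital signs at restart to Table 6-3. Neither cross-reference depends on why dosing stopped.

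**The concern.** Section 4.3.1 gives CRS mitigation as the reason for the step dose. Table 6-3 re-applies the step dose according to time off drug, not cause. A lead-in that sorts patients by cause cuts across that logic.

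Take two patients who have each gone 29 days since a later 10 mg dose. One was held for hepatitis B reactivation (Section 8.4.5.4), which is not in Table 6-2. On the literal text this patient restarts at 1 mg with premedication. The other was held for grade 3 neutropenia and has no stated restart dose. The schedule would give 10 mg, ten times as much. Section 2.3 names neutropenia as a key adverse drug reaction, so the second case is foreseeable. Two sites reading the same page could restart the same patient at different doses.

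**Working it through.** The plan gives no figure to reproduce. The check is of scope, then of whether the limits can be passed, then of what the other sections restore.

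**1. Scope.** Toxicity delays go to Table 6-2, and the next sentence covers all *other* delays. In that position, *other* means not handled in Table 6-2. A softer reading is that Table 6-2 displaces Table 6-3 only where it gives its own restart guidance. That still excludes grade 3 neutropenia, which has a restart cell.

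**2. Which entries can run long.** Most entries have a resolution limit that leads to discontinuation: 7 days for grade 2 or 3 CRS, grade 3 neurologic events and grade 4 neutropenia, and 5 days for grade 3 hypersensitivity. Grade 3 neutropenia and pituitary dysfunction have none. The seizure entry states no maximum of its own, but it sits with the neurologic events, whose grade 3 row has the 7-day limit. Hepatotoxicity goes to Section 11.7, where rechallenge is agreed case by case. TLS has a 14-day limit and is tested below.

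**3. Day counts.** Nominal days are C1D1 = 1, C1D8 = 8, C1D15 = 15 (window to day 16) and C2D1 = 29, then every 14 days. The event is assumed to be found on the dosing day, and gap = days from last dose to detection + days held.

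| Grade 3 neutropenia found at | Last dose | Gap | Limit |
|---|---|---|---|
| C1D8, lasts 8 days | step dose | 7 + 8 = 15 | 14 |
| C1D15, lasts 15 days | first 10 mg | 7 + 15 = 22 | 21 |
| later dose, lasts 15 days | later 10 mg | 14 + 15 = 29 | 28 |

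Each limit is passed.

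TLS after the step dose: Section 11.11.3 counts laboratory TLS up to 7 days after treatment starts, that is, to day 8. Onset on days 3 to 8 with resolution at the 14-day maximum falls on days 17 to 22, past the C1D15 window. Dosing on resolution gives a gap of 17 − 1 = 16 to 22 − 1 = 21 days. Waiting for C2D1 gives 29 − 1 = 28 days. All exceed 14.

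TLS after the first 10 mg dose: with onset by day 15, 15 + 14 = 29 and 29 − 8 = 21, which does not exceed 21. After a later dose: 14 + 14 = 28, which does not exceed 28. The TLS problem is therefore clear only after the step dose.

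**4. What other text restores.** Table 6-1 restores cycle 1 monitoring and Table 8-1 restores vital signs. For TLS, Table 6-2 adds first-dose monitoring and medical monitor consultation. None of these sets a restart dose or premedication.

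**5. The CRS figure in the protocol.** Section 4.4 reports, at 10 mg in Study 20200491, 40 + 27 + 1 = 68 of 133 patients with CRS, or 51.1%. Of the 68, 67 were grade 1 or 2, one was grade 3, and none was grade 4 or 5. Those patients received the step-dose regimen (Section 4.3.1).

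**The case against.** The best reply is that the gap is largely closed by intent. Table 6-3 has an unqualified title, its rows depend only on time since the last dose, and Tables 6-1 and 8-1 cite it for any extended interruption. A site must open Table 6-3 to learn whether cycle 1 monitoring applies, and the same cell tells it to repeat the step dose with premedication. Many sites would then do so. This stands as evidence of what was meant, and it limits how often the literal reading would be followed. It does not remove the conflict, because the sentence that sets the table's scope still says otherwise.

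Four stronger readings are tempting, and the documents do not support them:

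- *The protocol orders 10 mg after a long toxicity hold.* It does not. The 10 mg dose is inferred from the Table 6-1 schedule, which is not a restart rule.
- *Table 6-2 never addresses restart dose.* Grade 2 hypersensitivity resumes the remaining dose more slowly, and hepatotoxicity is routed to Section 11.7, which allows a reduced dose. The silence is specific to certain entries.
- *About half of such patients would have CRS.* The 51% is overall CRS under the normal step-dose regimen, mostly after the first two infusions. Nothing in the documents gives the risk of a 10 mg restart after a gap.
- *The Schedule of Activities forbids dexamethasone at restart.* Its restriction to cycle 1 describes routine dosing. Taken as a prohibition, it would also contradict Table 6-3 itself.

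**Conclusion.** The point holds as a conflict between the wording of one sentence and the evident purpose of the table it introduces. On the literal text, long holds for grade 3 neutropenia or pituitary dysfunction, and some TLS holds after the step dose, lose the repeat step dose and premedication. No restart dose is put in their place. Monitoring is not lost, so what remains is avoidable CRS risk under observation.

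The size cannot be stated. The protocol gives no rate of prolonged grade 3 neutropenia, G-CSF is permitted and may shorten holds, and about 30 patients are planned. The day counts assume nominal visits and, except for the C2D1 case, dosing on resolution. The conclusion also depends on a site following the lead-in as written. The change is still worth making, because it protects patients at small cost.

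**What to change.** Replace the lead-in to Table 6-3 with wording such as:

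*For all treatment interruptions or delays, including those under Table 6-2, once any Table 6-2 restart criteria are met, also apply the Table 6-3 limits: if the time since the last dose exceeds the limit, repeat the 1 mg step dose with cycle 1 premedication and monitoring. Any additional or stricter requirements in Table 6-2 or Section 11.7 (for example TLS monitoring, hypersensitivity premedication, same-day restart of a paused infusion at a lower rate, reduced-dose hepatotoxicity rechallenge) continue to apply.*

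Add *see also Table 6-3* to the neutropenia, pituitary and TLS restart text in Table 6-2.

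The second sentence of the new wording is needed. A blanket instruction to take dose, premedication and monitoring from Table 6-3 after every delay would override the listed safeguards, because below its limits Table 6-3 says only to go on at 10 mg.

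The cost is a short amendment or clarification letter. An affected patient has one extra monitored 1 mg visit and reaches 10 mg about one week later, as Table 6-3 already requires after other long delays.

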6.2.3 Hepatotoxicity Stopping and Rechallenge Rules

Refer to Section 11.7 for details regarding drug-induced liver injury guidelines, as specified in the Guidance for Industry Drug-Induced Liver Injury: Premarketing Clinical Evaluation, July 2009.

6.3 Preparation/Handling/Storage/Accountability

Guidance and information on drug preparation, handling, storage, and accountability for the investigational product, and noninvestigational product(s)/auxiliary medicinal product(s) will be provided to the site.

6.4 Method of Treatment Assignment

Subjects who meet eligibility criteria and enroll in the study will be assigned to treatment with tarlatamab.

6.5 Blinding

This is an open-label study; procedures to blind treatment assignment are not applicable.

6.6 Treatment Compliance

When subjects are dosed at the site, they will receive tarlatamab directly from the investigator or designee, under medical supervision. The date and time of each dose administered in the clinic will be recorded in the source documents and recorded on the CRF.

